## 2.2 BACKGROUND

Chronic obstructive pulmonary disease (COPD) is the 4th leading cause of death in the United States. It is characterized by fluctuating respiratory symptoms punctuated by transient acute worsening termed acute exacerbations of COPD (AECOPD). The optimal management of COPD requires accurate assessment of respiratory symptom burden, prevention, timely identification and early intervention on AECOPD ([www.GOLD.org](http://www.GOLD.org)). A key component of symptom management is the use of inhaled short-acting beta-agonists (SABA). Per treatment strategies, all individuals with spirometry-confirmed COPD (regardless of severity) should be prescribed SABA therapy. Accurate assessment of SABA use is essential in COPD, as it not only informs overall symptom control but also may also herald onset of an AECOPD event. Unfortunately, several studies have demonstrated that physicians are ineffective at accurately assessing SABA usage as a marker of disease control, as patients often misreport their actual use. Moreover, there are no technologies that could serve to automatically alert a patient or provider about abrupt increases in SABA use or decreases in inspiratory flow rate, which may both identify an impending AECOPD. Closing these assessment gaps through real-time electronic capture of SABA use has the potential to improve the assessment and care of COPD patients in the chronic setting and during acute decompensation.

There are several factors that can impact successful SABA administration. These include inhalation technique, duration, and inspiratory effort. Dry-powder inhalers (DPIs) are breath-actuated and tend to be easier for patients to use than metered dose inhaler or soft mist inhalers. However, there is emerging evidence that delivery from DPI may be suboptimal in some patients and settings. It has recently been shown that COPD patients can exhibit suboptimal peak inspiratory flow (PIF) in the stable outpatient setting (Ghosh, Sulaiman) and during hospital exacerbations (Loh, Sharma). Although published evidence regarding suboptimal delivery from DPIs in the COPD population is emerging, substantial knowledge gaps exist including the day to day variation in PIF in ambulatory COPD patients when clinically stable and during periods leading up to and recovery from AECOPD.

## 2.3 RISK/BENEFIT ASSESSMENT

### 2.3.1 KNOWN POTENTIAL RISKS

This study is considered low risk as all participants enrolled will already be using albuterol in their clinical care. Potential risks include albuterol side effects or loss of confidentiality.

Inhaled albuterol is the most commonly used rescue medication used in the COPD population as part of their normal clinical care. Standard doses of inhaled albuterol can cause transient cough, mild tachycardia, and tremors.

There is a chance of emotional distress if data from questionnaires or other home testing domains are not kept private. Safeguards are taken to ensure that subjects' confidentiality is maintained. General study measures include: 1) unique study numbers on documents containing de-identified data; 2) maintaining identifiers on linking file in a locked drawer in a private office; and 3) restricting access to files and

password protected databases to essential study personnel. All data are reported without personal identifiers. The study investigators, who will have access to the medical chart and personal data for study participants, have already received training and certification according to the institutions obligations under the Health Insurance Portability and Accountability Act (HIPAA). We will use unique study numbers. The linking form will be the only form linking study ID to personal data. This will be maintained in a locked drawer in a private office. We will maintain all other data linked to study ID on REDCap. All study related forms (regardless of identified or de-identified) will be placed in locked files and kept in a separate office from the linking file. Electronic data will be retained on a secure network via REDCap or password protected files.

The DAQApp provides patients with a Privacy Notice within the App explaining Teva's policies and practices for handling information and the choices that patients can make about the how their information is collected and used. Information that is collected and its use is described in detail in the Privacy Notice. Patients must accept the privacy notice within the App and provide in-App consent to store their information in a cloud prior to using the App functionality. Information stored may include inhalation events, inhalation metrics as well as DAQ App diagnostic data. Patients must also provide a separate consent to share their information with a specific healthcare provider or research study site by signing up to a restricted access "Healthcare Program" within the DAQ App. A healthcare provider or research study personnel can view the information via a web-based application, the Digihaler® Dashboard.

Teva has enacted commercially reasonable physical, technical, and administrative safeguards to secure information that is collected and stored on the Teva Digital System, which includes the App, the dashboard and the cloud. To prevent unauthorized access to their personal information, the App or any portion thereof, to maintain information accuracy, and to ensure the correct use of information, patients are strongly encouraged to password protect their device and refrain from providing any third party with unsupervised access to their device.

---

### 2.3.2 KNOWN POTENTIAL BENEFITS

There are no known individual benefits that are expected as a result of this trial. Rather, we expect that the benefit will be to society as a whole if this study helps to advance the understanding of the ProAir Digihaler in the COPD population.

---

### 2.3.3 ASSESSMENT OF POTENTIAL RISKS AND BENEFITS

Before participating in the study, subjects will be asked about history of intolerance to albuterol. The study team will also confirm that the participant is using albuterol on a regular basis (defined as at least one puff weekly for each of the last four weeks). If the safety of albuterol use cannot be assured, the subject will be excluded from the study.

---

## 3 OBJECTIVES

### Primary Objective:

- To determine the variation in ProAir Digihaler metrics (PIF, inhalation volume, number of inhalation events) amongst COPD patients in the ambulatory setting.

**Secondary Objectives.**

- To determine the correlation of self-reported SABA use with actual SABA use collected by the ProAir Digihaler.
- To determine the correlation of inhaler metrics (PIF, inhalation volume, number of inhalation events) with monthly CAT score domains.
- To determine the correlation of inhaler metrics (PIF, inhalation volume, number of inhalation events) with the daily self-assessment asking “How are you feeling?” with responses provided on a Leikert scale.

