**Description of Study****Intervention:**

In light of the COVID pandemic, this study is designed to be conducted entirely virtually to minimize any potential interruptions related to COVID. After identification and consenting, participants will be mailed the ProAir Dihihaler (provided by Teva). The study coordinator will contact the participant to ensure set-up and correct usage. Participants will be asked to use the ProAir Dihihaler as their primary mode of SABA therapy as they would in usual treatment and indicated in the product package insert and Instructions for Use. They will be provided a COPD Action Plan to ensure they have appropriate instructions to handle a possible AECOPD. They will answer a daily self-assessment asking "How are you feeling?" with responses provided on a Leikert scale on the DAQ App, as well as Dihihaler metric algorithm-triggered DAQ on the DAQ app. The DAQ will collect yes/no responses to questions focused on change in respiratory symptoms, sleep disturbances, daily activity limitation, and anxiousness.. The participants will be contacted once per month to collect CAT score and self-reported average albuterol use over the preceding month. They will also be asked about any AECOPD events requiring treatment with antibiotics and/or steroids or hospitalization in the prior month. Participants will be enrolled for three months duration. All individuals will be provided three inhalers at enrollment. In the event their ProAir Dihihaler does not last three months, they will be prescribed another ProAir Dihihaler (provided by Teva).

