**4 STUDY DESIGN****4.1 OVERALL DESIGN**

This is a multisite, observational, 3-month pilot study of ProAir Digihaler use in 60 COPD patients at-risk for AECOPD. Participants will be recruited from two sites (Wake Forest University, N=30; University of North Carolina at Chapel Hill, N=30). All participants will have spirometry-confirmed COPD with an increased AECOPD risk (defined as two moderate or one severe AECOPD in the last 12 months).

Participants will be recruited from existing clinical pools at both sites including COPD registries, virtual and in-person outpatient clinics (routine or post-hospital discharge). Although this study will not be powered to make meaningful assessments of inhaler metric changes at the time of an AECOPD, we are permitting patients recently discharged for an AECOPD event to be enrolled, which will permit assessment of changes during the recovery phase as well as enrich for individuals more likely to have an AECOPD event during study.

In light of the COVID pandemic, this study is designed to be conducted entirely virtually to minimize any potential interruptions related to COVID. Both UNC and Wake Forest have experience conducting virtual studies with local IRB approval. Potentially eligible patients will be identified and screened for possible inclusion through existing registry review, virtual clinic visits or in-person visits.

Potentially eligible participants will be contacted, with the permission of their care providers, by study investigators or research coordinators and assessed for interest. Based on local IRB approval, they will either be mailed an informed consent (ICF) for phone review with the research coordinator or will complete verbal consent over the phone. After consenting, participants will be mailed the ProAir Digihaler (provided by Teva) The study coordinator will contact the participant to ensure set-up and correct usage.

Participants will then be asked to use the ProAir Digihaler as their primary mode of SABA therapy as they would in usual treatment and indicated in the product package insert and Instructions for Use. They will be provided a COPD Action Plan to ensure they have appropriate instructions to handle a possible AECOPD. They will answer a daily self-assessment asking "How are you feeling?" with responses provided on a Leikert scale on the DAQ App, as well as Digihaler metric algorithm-triggered DAQ on the DAQ app.

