The participants will be contacted once per month to collect CAT score and self-reported average albuterol use over the preceding month. They will also be asked about any AECOPD events requiring treatment with antibiotics or steroids in the prior month. If there is evidence during the calls of clinical deterioration by self report or an abrupt increase in CAT by > 4 units patients will be advised to contact their primary care or COPD provider.

Participants will be enrolled for three months duration. In the event the participant has an AECOPD within two weeks of end of study, they will be followed for 14 days after AECOPD resolution. Total participant duration is three months (+21 days to account for 14 days in event of AECOPD and seven day window at end of study). In the event their ProAir Digihaler does not last three months, they will be prescribed another device (provided by Teva). Hospital admission during the course of the study will not prohibit continued participation.

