## 9 STATISTICAL CONSIDERATIONS

### 9.1 HYPOTHESIS

We hypothesize that inhaler metrics (PIF, inhalation volume, rescue inhaler use) will vary among COPD populations. We also hypothesize that increased albuterol use will positively correlate with worse daily Leikert scores, declining PIF, lower inhalation volume and higher CAT scores. We hypothesize that self-reported albuterol use will be lower than actual albuterol use captured by the DAQ app. We hypothesize that increased albuterol use will positively correlate with more symptomatic DAQ responses. The proposed study is designed to yield an initial exploration of the metrics captures by the Digihaler in a COPD population.

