### 9.4 STATISTICAL ANALYSES

Below are the pre-specific outcome measures:

Primary Outcome Measure:

1. Variability in Peak Inspiratory Flow (PIF) Measured via Digihaler Device (Time Frame: Three months)
  - b. PIF is the maximal flow occurring during an inhalation effort, expressed in Liters/minute. Mean, standard deviation and coefficient of variation (calculated by dividing standard deviation of PIF by the mean of the PIF) of daily PIF measurement collected over three months will be calculated. PIF will be measured using the Digihaler device.

Secondary Outcome Measures:

1. Correlation of Self-Reported Inhaler Use with Actual Inhaler Use (Time Frame: 3 months)

- a. Correlation between self-reported inhaler use and actual inhaler use over three months will be calculated with Spearman rank-order correlation coefficient. Self-reported inhaler use will be determined with an investigator-developed single question categorizing average use over the last four weeks with five groups (not at all, once a week or less, two or three times a week, one or two times a day, three or more times a day). Actual inhaler use will be directly measured via Digihaler device and categorized into one of the five groups described above.
2. Variability in Inhalation Volume Measured via Digihaler (Time Frame: Three months)
  - a. Inhalation volume is the volume of air inspired during an inhalation effort, expressed in Liters. The mean, standard deviation and coefficient of variation (calculated by dividing standard deviation of inhalation volume by the mean of the inhalation volume) of daily inhalation volume measurements collected daily over three months will be calculated. Inhalation volume will be measured using the Digihaler device.

The primary analysis will be descriptive, with analytical plans as defined above for each primary and secondary outcome.

The primary analysis will be descriptive, with analytical plans as defined above for each primary and secondary outcome.

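### Section 9.1 predicts under-reporting of albuterol use, but the only planned comparison, a Spearman coefficient, cannot show it

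*Combined protocol and SAP*

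**What the plan says.** Section 3 lists the secondary objective "To determine the correlation of self-reported SABA use with actual SABA use collected by the ProAir Digihaler". Section 9.1 goes further than correlation: "We hypothesize that self-reported albuterol use will be lower than actual albuterol use captured by the DAQ app".

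Section 9.4 (and the outcome measures in Section 1.1) uses one self-report question on average use over the last four weeks, with five groups running from no use to three or more times a day. For the other side, "Actual inhaler use will be directly measured via Digihaler device and categorized into one of the five groups described above". The correlation between the two "will be calculated with Spearman rank-order correlation coefficient". The exploratory list in Section 9.4 describes SABA utilization but contains no paired difference, agreement or direction summary of self-report against device.

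Three further provisions bear on what is being compared:

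- The self-report groups count times. The device counts inhalation events, and Section 6.1.2 describes an administration as 2 inhalations. No section converts one to the other.
- Section 4.1 asks participants to "use the ProAir Digihaler as their primary mode of SABA therapy". Section 6.3 disallows no medication, Section 5.2 has no nebulizer criterion, and the rationale in Section 10.4 calls nebulizer use frequent without naming a drug or a rate.
- The monthly item is described in Section 4.1 as "self-reported average albuterol use over the preceding month", but in Section 9.4 as inhaler use. Its scope is not stated.

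**The concern.** Section 2.2 motivates the work by noting that "patients often misreport their actual use". Misreporting in a stated direction is a question about differences between paired values. A Spearman coefficient answers another question: whether participants who report more also use more. If everyone under-reports by a similar proportion, the ranks hardly change and the coefficient stays high. A high value could then be read as evidence that self-report is accurate, when it is equally compatible with marked under-reporting. A secondary outcome would be reported in full while the hypothesis attached to it went unexamined.

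The obvious repair, a paired table, has a trap of its own. If each recorded inhalation is taken as one time, a participant who takes two inhalations on each occasion and reports the occasions correctly will fall in a lower self-report group than device group. The hypothesis would then be confirmed by the units alone.

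**Working it through.** The plan gives no figure to reproduce: Section 9.2 states no power calculation, and no correlation or misreporting rate is assumed. From the documents come n=60 (Section 5.4), the five groups and the Spearman coefficient (Section 9.4), and 2 inhalations per administration (Section 6.1.2). Everything else below is an assumption.

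**Step 1. A pure shift.** Put 15 participants in each of four adjacent device groups (4 × 15 = 60) and let each report exactly one group too low. The ranks are unchanged, so rho = 1.00, the same as under perfect agreement. The mean paired difference is −1.0 group.

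**Step 2. Proportional under-reporting with recall error.** Total use T per week is lognormal (median 7, log-SD 1). Self-report is R = T × b × exp(e), with e normal (mean 0, SD 0.4). Device use is D = T. Both are cut at 0.25, 1.5, 5 and 17.5 uses per week.

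| Reported/true ratio b | Spearman rho | In a lower self-report group |
|---|---|---|
| 1.0 | 0.83 | 12% |
| 0.8 | 0.82 | 23% |
| 0.5 | 0.81 | 53% |

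The 95% sampling range of rho at n=60 is about 0.71 to 0.91, so these three values cannot be told apart. A second set of assumptions (0.5 plus a gamma variable with mean 14 uses per week, two choices of cut-point) gives the same picture. For ratios 1.0, 0.7 and 0.5, rho is 0.82–0.85, 0.81–0.84 and 0.78–0.83, while the lower share is 11–12%, 27–30% and 47–52%.

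**Step 3. Inhalations against times.** Same model, accurate reporting (b = 1), no other SABA, device count = k × T.

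| Recorded inhalations per time, k | Lower self-report group | Higher |
|---|---|---|
| 1.5 | 33% | 2% |
| 2 | 50% | 0.4% |

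This apparent under-reporting is entirely a product of the units.

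**Step 4. Gaps between groups.** Two or three times a week ends at 3 and one or two times a day starts at 7 × 1 = 7, so averages of 4 to 6 a week have no group. Likewise 7 × 2 = 14 and 7 × 3 = 21 leave 15 to 20 a week unassigned. Step 2 splits these gaps by assumption; the plan has no rule.

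**Step 5. Off-device SABA.** Suppose the item is answered for all albuterol and true under-reporting is 20%. A fraction f of participants takes a share s off the device, so D = T × (1 − s) for them.

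| f, s | rho | Lower v higher |
|---|---|---|
| none | 0.82 | 23% v 5% |
| 20%, 25% | 0.81–0.83 | 20% v 7% |
| 40%, 50% | 0.77–0.78 | 14% v 18% |

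A 50% share is the limit of what primary mode can mean. The second set of assumptions, which lets individual shares exceed that limit, lowers rho from 0.82–0.85 to 0.73–0.75 with half of participants affected and unbiased reporting. If the item is understood as Digihaler use only, the case f = 40%, s = 50% returns to 23% v 5%: no distortion.

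**Step 6. Precision of the added table.** 14/60 = 23%; the exact 95% CI is 13% to 36%.

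**The case against.** The plan is a descriptive pilot that Section 9.1 itself calls an initial exploration. The objective asks for a correlation, and a correlation is what will be computed. Both five-group variables are collected anyway, so a paired table can be produced later without new data. That is right about the data, and it keeps the point modest. It does not remove it. The conversion of inhalations to times and the handling of the gaps can decide the answer, as Steps 3 and 4 show, and they should be fixed before the comparison is seen.

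A reader might infer something stronger: that permitted nebulizer use invalidates the self-report comparison or hides under-reporting. The documents do not support this.

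- Section 10.4 gives neither the nebulized drug nor a rate, so every share in Step 5 is assumed. At modest shares the direction survives.
- Section 9.4 labels both sides inhaler use, and Section 5.1 requires willingness to switch the rescue device. On that reading the bias vanishes.
- The questionnaire named in Section 6.1.1 is not reproduced and may settle the scope.
- Section 1.3 lists inhaler use and compliance at the calls, and Section 10.1.9.1 mentions concomitant medications. Neither passage plans a count of other SABA or an analysis using it, but some information may exist.

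What stands of the off-device argument is a matter of labelling and scope. It is also fair to object that rewording the item now could mix two instruments: the rationale in Section 10.4 indicates that recruitment had begun. Nor could Digihaler-only wording apply at enrollment, before the device is supplied. The fix respects both limits.

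**Conclusion.** The directional hypothesis in Section 9.1 is not examined by any planned analysis. This rests on a property of rank correlation and needs no assumption about the cohort; the simulation only shows how little the coefficient moves (0.83 to 0.81) while under-reporting goes from none to 50%. A paired summary would fill the gap, but only once inhalations are mapped to times; otherwise accurate reporters can look like under-reporters (50% v 0.4% at an assumed two inhalations per time).

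The off-device point is secondary. Other SABA is permitted and not counted, so actual SABA use is too broad a name for the device count. The size and even the presence of a bias cannot be established from the documents. Under Step 5 the coefficient falls from 0.82 to 0.77–0.78 at most within the primary-mode limit, inside its sampling range. PIF and inhalation volume per recorded inhalation are not affected.

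**What to change.** Change the analysis plan and labels only.

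1. Keep the Spearman coefficient. Add a paired description: percent of participants in a lower, same or higher self-report group than device group, each with a 95% CI. State how the monthly answers enter, so that each participant counts once per table.
2. Before that, prespecify how recorded inhalations are converted to times (for example, by grouping inhalations close together into one use event) and how averages falling between the groups, such as 4 to 6 a week, are assigned. Include a sensitivity analysis to the conversion.
3. Call the comparator Digihaler-recorded use, and state whether the on-study item covers the Digihaler, all inhaled SABA or all albuterol.
4. If feasible, record other SABA use at the existing monthly calls, for a supportive sensitivity analysis. Do not reword the item mid-study for participants already enrolled.

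Cost: items 1 to 3 need no new data, only some extra analysis and text. Item 4 lengthens the calls slightly and is itself self-reported. A restricted analysis would be small: if 40% reported other SABA (an assumption), 60 × 0.6 = 36 would remain. The percentages will be imprecise at n=60, which suits a descriptive pilot as long as the intervals are shown.
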